ICL: Imaging Core Laboratory

IFN- γ : Interferon gamma

MMP-9: Matrix metallopeptidase 9

MTD: Maximum Transverse Diameter

SAP: Statistical Analysis Plan

SF-36: The Short Form (36) Health Survey

Non-Invasive Treatment of Abdominal Aortic Aneurysm Clinical Trial

N-TA³CT

STATISTICAL ANALYSIS PLAN

3 Introduction

This Statistical Analysis Plan (SAP) describes the analyses to be conducted for the primary endpoint of the Non-Invasive Treatment of Abdominal Aortic Aneurysm Clinical Trial (N-TA³CT).

3.1 Primary Aim:

Determine if doxycycline (100 mg bid) will inhibit the increase in greatest transverse diameter of small abdominal aortic aneurysms (3.5-5.0 cm in men, 3.5-4.5 cm in women) over a 24-month period of observation in comparison to a placebo-treated control group.

3.2 Endpoints

The primary outcome is the change in abdominal aortic aneurysm maximum transverse diameter (MTD) on CT scan from baseline to the follow-up assessment CT scan two years after randomization, as measured in the Imaging Core Laboratory (ICL).

Secondary outcomes will derive from central ICL analyses of the CT scans performed every six months on patients and from the clinical follow-up of randomized patients, from clinical observation, local laboratory findings, study visit quality of life assessments, and from biomarker analyses to be performed in the Biomarkers Core Laboratory (e.g., changes from initial MMP-9 levels, and MMP-9 levels at 24 months of follow-up).

3.3 Study Design

3.3.1 Study population

The study population will include patients 55 years of age or older who are found to have small (3.5-5.0 cm among men and 3.5 - 4.5 cm among women in the largest transverse diameter) abdominal aortic aneurysms on quantitative CT scans.

Patients will be excluded from the study if they are unable to give their own informed consent to participate; have symptoms related to abdominal aortic aneurysm; have other intra-abdominal vascular pathology that may require repair within 24 months (e.g., renal artery stenosis, large iliac artery aneurysms, iliac occlusive disease, aneurysmal involvement of the renal artery); have had previous abdominal aortic aneurysm repair by

Non-Invasive Treatment of Abdominal Aortic Aneurysm Clinical Trial

N-TA³CT

STATISTICAL ANALYSIS PLAN

open surgical or endovascular technique; have an active malignancy with life expectancy less than two years; have an allergy to tetracycline; are currently or have been recently treated (previous six months) with tetracycline derivatives; they are currently taking anti-seizure medicines metabolized by pathways influenced by doxycyclines (e.g., carbamazepine, phenytoin, and barbiturates); stage II hypertension (patients whose blood pressure is persistently in the range of systolic > 160 mm Hg or diastolic > 100 mm Hg despite primary physician's best effort to achieve adequate therapy); have dialysis dependent renal failure or impending dialysis treatment for renal insufficiency; have a chronic infection requiring long-term (> 2 weeks) antibiotics, have known genetic syndromes responsible for the abdominal aortic aneurysm (e.g., Marfan's Syndrome), are under treatment with systemic immunosuppressive agents, could become pregnant, are not good candidates for clinical trial participation or are enrolled in another clinical trial.

3.3.2 Treatment groups and dosing

Patients will be assigned to doxycycline 100 mg p.o., b.i.d., or matching placebo. Patients randomly assigned to doxycycline will receive bottles containing a sufficient supply of 100 mg doxycycline capsules to take one capsule twice a day until the next appointment (about 100 days). Patients randomly assigned to placebo will receive a similar appearing supply of placebo capsules.

3.3.3 Study visits and assessments, study baseline

Under the original protocol, participants were to be followed in-clinic every 3 months until a common termination when the last participant randomized had been followed for 24 months. Under Protocol Revision 1.6.0, participants are expected to have 10 visits for this study: one baseline, eight at quarterly intervals while on treatment, and one post-treatment follow-up. Follow-ups will be conducted as in-clinic visits except that at 9, 15 and 21 months they *may* be conducted by telephone. The appendix of the protocol contains a summary of the timing of the visits and the assessments and data that are collected at each visit.

3.3.4 Randomization and Blinding or Masking

The DCC staff prepared randomization schedules for each Clinical Site participating in N-TA³CT. The program for generating randomization schedules has the following characteristics: 1. There will be two randomization strata – one for men and one for women – at each clinical site; 2. Treatments are assigned in random order within blocks sizes two, four, six or eight with equal numbers of patients assigned to the doxycycline or placebo within each block. 3. Block sizes (two to eight patients per block) are randomly selected with the probability of each block size specified by DCC staff.

The DCC staff maintained a web-based randomization system for Clinical Site staff to request treatment allocations as eligible patients are identified. Only study-certified clinic staff with individually assigned userid/password can access the randomization and drug dispensing

Non-Invasive Treatment of Abdominal Aortic Aneurysm Clinical Trial

N-TA³CT

STATISTICAL ANALYSIS PLAN

application. At randomization, after selecting the participant ID to randomize, clinic site staff are asked to enter the participant's "letter code", gender and date of birth. These are verified against the data entered into the electronic data capture application for this participant. Only participants meeting the inclusion/exclusion criteria according to data entered in the eDC system, with a CT scan read by the Imaging Core Laboratory confirming eligibility, and with complete baseline data, including record of collection of the baseline biomarker sample are listed among the participant IDs eligible for randomization. The date and time of the completion of the randomization treatment assignment is the time of study entry for each patient.

In the Clinical Sites, Clinical Coordinating Center, Imaging Core Laboratory and Biomarkers Core Laboratory, the patients, directors (i.e., Clinical Site lead investigator), clinical site coordinators, and other study staff involved with direct patient care will be blinded to treatment assignments. Staff of the Data Coordinating Center will have access to individual patient treatment assignment on a "need-to-know" basis. The DSMB, the Director of the Data Coordinating Center will remain blinded to individual participant treatment assignment and to by-treatment-arm interim results. Only Data Coordinating Center staff involved in the production and distribution of the Closed Report to the DSMB or development and maintenance of the randomization system will have access to treatment code assignments and by-treatment-arm results.

The Data Coordinating Center will maintain records of each patient's treatment assignment.

3.3.5 Sample Size and Power

The study is designed to have greater than 90% power with a total sample size of 248 patients for a one-sided 0.025 test for an assumed reduction of 40% in the mean increase in aneurysm diameter from 2.5 mm/year to 1.5 mm/year. The calculations allow for a 10% non-adherence rate in the doxycycline treatment group and for 15% of participants to have a missing two-year CT scans. Additional details regarding the sample size and power calculations are contained in the protocol.

4 General Consideration for Data Analyses

4.1 Analysis Populations

4.1.1 Intention to Treat

The intention-to-treat population includes all patients randomized, analyzed by treatment assigned at randomization.

4.1.2 Full Analysis Population

The full analysis population includes all patients randomized except those with no follow-up contact and no follow-up CT scan, analyzed by treatment assigned at randomization. Because

Non-Invasive Treatment of Abdominal Aortic Aneurysm Clinical Trial

N-TA³CT

STATISTICAL ANALYSIS PLAN

treatment was never started and because the primary endpoint is not known and cannot be reasonably imputed in participants with no follow-up and no follow-up CT scan, analysis of the primary endpoint will be conducted on the *full analysis population*.

4.1.3 Per-Protocol Population

A per-protocol population will be defined as all participants randomized who

1. Complete 24 months of follow-up with a 2-year CT scan available for analysis;
2. Or undergo repair within 24 months (+ 90 days) of randomization;
3. Or die or suffer rupture of their AAA within 24 months (+90 days) of randomization;
4. And reported to have taken at least 80% of their expected study drug doses over the course of their follow-up period.

4.2 Statistical Analysis Issues

4.2.1 Strata and Covariates

Randomization is stratified by gender and site. Gender will be included in the primary efficacy analysis model.

4.2.2 Multiple Comparisons

For the primary analysis, we consider a one-sided p-value of 0.0247 to be significant. It is less than 0.025 to account for the interim analyses. To account for the multiplicity of hypotheses being tested in secondary and exploratory analyses, a p-value < 0.01 will be required to consider there to be evidence of differences present, i.e. to reject the null hypothesis. We consider p<0.001 as strong evidence.

4.2.3 Multi-center Studies

There are a total of 22 sites participating in the study. Analyses will not adjust for site.

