The change in normal score from baseline -- i.e., the two-year normal score for patients randomized to doxycycline and placebo minus the baseline normal score -- will be analyzed using a linear regression model (analysis of covariance -- ANCOVA), with variables for the randomized treatment assignment (0 for placebo, 1 for doxycycline), the normal score for baseline diameter, and gender in the model.

Prior to performing the primary outcome analysis, an interaction term for the randomization stratum (gender) with treatment assignment will be assessed in the ANCOVA model. If there is significant (at two-sided $\alpha=0.05$) evidence of differences in the effect of treatment according to gender, other than a small quantitative difference (less than half a normal score difference in treatment effect) between effects that are in the same direction for each gender, the analysis will be performed separately for men and for women. In the event of a treatment by gender interaction being observed, we will review study results by gender to determine the nature of the differences in treatment effects. If there is no interaction, the ANCOVA will be used to estimate the overall treatment effects across all clinical sites and both strata (genders). The primary analysis will be performed on the normal scores corresponding to percentile rank of each patient at baseline and follow-up.

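### Randomisation is stratified by site but no analysis adjusts for site, so the primary test is valid but mildly conservative if sites differ

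*SAP*

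**What the plan says.** Section 4.2.1 names two stratification factors, "Randomization is stratified by gender and site", and carries one into the model: "Gender will be included in the primary efficacy analysis model". Section 3.3.4 describes a separate schedule for each site, with a stratum for men and one for women. Within each stratum, "Treatments are assigned in random order within blocks sizes two, four, six or eight with equal numbers of patients" on each arm.

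Section 4.2.3 reads "There are a total of 22 sites participating in the study", followed by "Analyses will not adjust for site". No reason is given. Section 8.1 is consistent with this: the ANCOVA is fitted "with variables for the randomized treatment assignment (0 for placebo, 1 for doxycycline), the normal score for baseline diameter, and gender in the model". The threshold is in section 4.2.2: "For the primary analysis, we consider a one-sided p-value of 0.0247 to be significant".

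Site returns only in section 9. There its influence on the treatment effect is to be inspected, outlying sites explained, and any inhomogeneity shown beside the primary result. That inspection does not change the primary model or its standard error.

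**The concern.** Permuted blocks within site make the arms nearly equal in number at every site, so differences in mean outcome between sites largely cancel out of the treatment comparison. An analysis that omits site does not know this. It counts between-site variance as residual noise and reports a standard error for a less balanced design than the one used. Confidence intervals are then wider, and p-values larger, than the design warrants.

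This bears on how the SAP reads a negative result. Section 9 makes the investigators responsible, if the null is not rejected, for showing that the test was sensitive. It also treats non-rejection as possible evidence against a 40% effect. Avoidable conservatism weakens that reading.

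Site differences are possible even though all scans are read centrally. The ranked outcome also includes death, rupture and endovascular repair, and both case mix and the decision to repair may vary by site.

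**Working it through.** **Inputs from the SAP.** 22 sites and two sexes give 22 × 2 = 44 strata. With 248 patients that is 248/44 ≈ 5.6 per stratum. Blocks are of 2, 4, 6 or 8, allocation is 1:1, and the one-sided level is 0.0247. Section 3.3.5 gives power above 90%, a fall from 2.5 to 1.5 mm/year, 10% non-adherence and 15% missing scans.

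**Assumed.** Site ICC from 0 to 0.20, meaning the share of residual variance due to site after baseline and sex, with total residual variance held fixed; 15% women; even or uneven site sizes.

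**The plan's own figure.** The stated power cannot be reproduced, because the SAP gives no standard deviation and refers to the protocol for details. It can only be inverted at 90%, using SD = δ·√(n/2)/(1.960 + 1.282):
- δ = 2.0 × 0.9 = 1.8 mm and n = 124 × 0.85 = 105.4 per arm: SD = 1.8 × √52.7/3.242 ≈ 4.03 mm.
- δ = 2.0 mm and n = 124 per arm: SD = 2.0 × √62/3.242 ≈ 4.86 mm.

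**Upper limit on the overstatement.** With perfect balance within site, the true variance of the contrast is about 4σ²(1 − ICC)/N, while the model without site reports about 4σ²/N. The ratio of reported to true standard error is then 1/√(1 − ICC): 1.010, 1.026, 1.054 and 1.118 at ICC 0.02, 0.05, 0.10 and 0.20. Unfinished blocks in small strata leave some imbalance, so the real ratios should be lower.

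**Planned model, simulated.** 20,000 trials per ICC, 248 patients, uneven sites, normally distributed outcome:

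| ICC | Reported SE / true SE | Actual one-sided level (nominal 0.0247) |
|---|---|---|
| 0 | 1.000 | 0.0251 |
| 0.02 | 1.008 | 0.0244 |
| 0.05 | 1.020 | 0.0231 |
| 0.10 | 1.040 | 0.0213 |
| 0.20 | 1.086 | 0.0174 |

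Monte Carlo error of the level is about 0.001. Even site sizes give similar ratios: 1.011, 1.031 and 1.077 at ICC 0.05, 0.10 and 0.20.

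**Random site intercept, simulated.** REML on normal scores, 248 patients, uneven sites, effect set for about 90% power; 12,000 null and 4,500 alternative trials per ICC:

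| ICC | Level, planned | Level, random site | Power, planned → random site |
|---|---|---|---|
| 0 | 0.0245 | 0.0251 | 89.8% → 89.9% |
| 0.02 | 0.0239 | 0.0252 | 89.9% → 90.1% |
| 0.05 | 0.0223 | 0.0246 | 89.8% → 90.6% |
| 0.10 | 0.0198 | 0.0247 | 90.8% → 92.6% |
| 0.15 | 0.0177 | 0.0236 | 90.5% → 92.9% |

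Monte Carlo error of the level is √(0.0247 × 0.9753/12,000) ≈ 0.0014, so the random-intercept model holds the nominal level. Two further simulations (1,500 and 6,000 trials per setting) gave gains of 0.1 and 0.05 points at ICC 0, 0.9 and 0.7 at 0.05, and 1.5 and 1.5 at 0.10.

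**Fixed site effects, for comparison.** With 211 evaluable patients (248 × 0.85), power without → with site was 89.8% → 88.5% at ICC 0, 90.3% → 90.0% at 0.05, 90.6% → 91.7% at 0.10 and 91.7% → 94.4% at 0.20. They cost power when sites do not differ.

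**The case against.** The plan is open and consistent: sex stays in, site stays out, and sections 4.2.1, 4.2.3 and 8.1 agree. Prespecifying a valid, slightly conservative test with under six patients per stratum is defensible. The gain is small at the ICCs most easily believed after baseline adjustment and central reading, and nothing in the SAP supports an ICC of 0.10 or more. The estimate itself hardly becomes more precise: its empirical SD at ICC 0.05 was 0.1146 without site and 0.1144 with the random intercept. The gain comes almost entirely from reporting the right standard error. All of this stands, and it limits the point to efficiency.

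It is also fair that a random intercept needs more than one line of code. Section 8.1.1 fixes complete-data degrees of freedom for an ordinary regression, and the imputation model has no site term. The site variance was estimated at zero in 57%, 31% and 12% of simulated trials at ICC 0, 0.02 and 0.05, so imputed data sets may differ on this. The fix has to cover these matters.

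Some stronger readings are tempting but not supported:
- **The test is invalid.** The error is on the safe side; the level falls below 0.0247 as sites differ.
- **The planned power is lost.** Power under the planned model with 211 evaluable patients rises from 89.8% at ICC 0 to 91.7% at 0.20. The shortfall is only relative to a model with site.
- **Site is ignored altogether.** Section 9 inspects its influence, though without adjustment.
- **Site was left out to save degrees of freedom.** The SAP does not say so; it gives no reason.

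**Conclusion.** The point holds as a modest efficiency and consistency issue. One of the two stratification factors is left out of every model without explanation, and if site means differ after baseline diameter and sex, the reported standard error is too large and the primary test mildly conservative. The overstatement is about 1-2% at ICC 0.02-0.05, about 4% at 0.10 and 8-9% at 0.20. A random site intercept recovers about 0-1 point of power up to ICC 0.05 and about 1.5-2 points at 0.10, with no loss seen at ICC 0.

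The direction is certain; the size is not, because the ICC is assumed. The simulations used a normal outcome or normal scores without the imputation step, so the figures show the order of magnitude only.

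**What to change.** In section 4.2.3, replace "Analyses will not adjust for site" with:

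> The primary ANCOVA (8.1), its interaction test, the interim analyses of the primary endpoint and the analyses in 8.2 and 8.3 include gender and a random intercept for clinical site; where the site variance is estimated as zero the model reduces to the ANCOVA without site.

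Then:
- add the random intercept to the model description in 8.1;
- replace the complete-data degrees of freedom in 8.1.1 with a rule suited to the mixed model, and state that the zero-variance rule applies within each imputed data set;
- consider site in the imputation model, so that imputed scans are consistent with the analysis.

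The cost is slightly more programming and a degrees-of-freedom rule; no new data are needed. Fixed site effects are not proposed, because they cost about one point of power when sites do not differ (89.8% to 88.5%). If the sponsor prefers to leave site out, the SAP should say why and acknowledge that the test is then mildly conservative.

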4.2.4 Study Baseline and Visits

Study baseline corresponds to measurements collected at the baseline visit, prior to randomization and initiation of treatment. Follow-up visits are scheduled based on the date of randomization and are expected to occur 45 days before or after the target time-point; 90 days are allowed for CT scans or primary outcome clinical events (i.e., death or surgical repair).

5 Interim Analysis and Data Safety and Monitoring Board

Two formal interim analyses will be performed: one when approximately the first third of outcome data is available and the next when approximately the second third of outcome data is available. Formal rules for stopping for efficacy, futility, or harm are described in the protocol.

In addition, at each DSMB meeting an analysis of six-month CT scan results will be presented. The DSMB may recommend early termination if the aneurysm growth is higher in patients receiving doxycycline than in placebo recipients, with a one-sided p-value less than or equal to 0.05 ($Z = 1.645$).

6 Subject Disposition

6.1 Disposition of Participants

A CONSORT diagram (<https://www.consort-statement.org/consort-statement/flow-diagram>) will depict the disposition of all participants screened and randomized.

6.2 Extent of Exposure

Compliance with assigned treatment arm will be assessed by capsule counts at each follow-up visit. For the full analysis set, for each treatment arm and visit, the percentages of patients who have taken greater than or equal to 80% of the expected capsules, based on the capsule count, will be reported.

Plasma samples will be collected approximately every six months. For patients assigned to doxycycline, these samples will be analyzed for measurement of doxycycline levels. At each of the four six-month time points, the percentages of patients on the doxycycline arm with detected doxycycline will be reported, along with mean, standard deviation, median and interquartile range of the doxycycline values.

Time to permanent discontinuation of study drug will be depicted by Kaplan-Meier plot comparing the two treatment arms.

6.3 Protocol Violations

Protocol violations will be reported for the full analysis population using counts and percentages of violations. The difference in count between the intention to treat population and the full analysis population will be presented.

7 Baseline Data

7.1 Demographics and Baseline Characteristics

Baseline characteristics by treatment group for the intention-to-treat population will be compared using counts, percentages and for continuous variables, descriptive statistics. The following characteristics will be reported: gender, age (mean, standard deviation, median and interquartile range), ethnicity, race, maximum diameter and volume of AAA separately by gender (most recent prior to baseline with mean, standard deviation, median and interquartile range), vital signs including systolic and diastolic blood pressure, height, weight and BMI by gender, medical histories, concomitant medications, baseline quality of life as measured by the SF-36 Quality of Life instrument, and baseline biomarker levels. Characteristics will be reviewed for the full analysis population as well.

8 Efficacy Analyses

8.1 Primary Efficacy Analysis

The primary analysis will be performed to test the null hypothesis of no difference in growth of abdominal aortic aneurysms between the two treatment groups (doxycycline and placebo) after 24 months of follow-up as measured by CT scans analyzed in the Imaging Core Laboratory. This analysis will use the full analysis population. In order to include patients whose 24-month abdominal CT scans are missing because of death, endovascular repair or for other reasons in the primary analysis, we will base our analysis on normal scores for percentile of rank status. We will assign worst ranks to deaths, in order of time from study entry to death, next worst ranks to rupture, next worst ranks to endovascular repair for clinical presentation, next worst ranks to endovascular repair for reasons of aneurysm growth beyond 5.5 cm in men or 5.0 cm in women or other presentation free of clinical indication, all in order of time from study entry within category. The order of ranks are summarized in Table 1. Clinical presentation will be assessed by the three vascular surgeon Principal Investigators, blinded to treatment assignment, independently; agreement by two of the three or all three will be taken as final. Outcomes for patients missing the 24-month CT scan will be imputed, as described in the next section.

Table 1. Summary of ranks.

Order of rank assignment (worst to best)	Description
1	Death (from day of study entry to day of death)
2	Aneurysm rupture (from day of study entry to day of repair)
3	Endovascular repair for reasons related to clinical presentation (from day of study entry to day of repair)

Non-Invasive Treatment of Abdominal Aortic Aneurysm Clinical Trial

N-TA³CT

STATISTICAL ANALYSIS PLAN

4	Endovascular repair for growth beyond 5.5 cm in men or 5.0 cm in women or other presentation free of clinical indication (from day of study entry to day of repair)
5	Change from baseline in largest, transverse diameter of the aneurysm, using normal scores as described below.

The ranks for patients assigned to doxycycline will be compared to the ranks of patients assigned to placebo using normal scores. If N is the total number of randomized patients, a rank of k will be assigned the value corresponding to $k/(N+1)$ in a standard normal distribution; for example, a rank of 100 out of 248 patients will receive the rank score corresponding to 0.4016, or a normal score $z = 0.2492$.

The change in normal score from baseline -- i.e., the two-year normal score for patients randomized to doxycycline and placebo minus the baseline normal score -- will be analyzed using a linear regression model (analysis of covariance -- ANCOVA), with variables for the randomized treatment assignment (0 for placebo, 1 for doxycycline), the normal score for baseline diameter, and gender in the model.

Prior to performing the primary outcome analysis, an interaction term for the randomization stratum (gender) with treatment assignment will be assessed in the ANCOVA model. If there is significant (at two-sided $\alpha=0.05$) evidence of differences in the effect of treatment according to gender, other than a small quantitative difference (less than half a normal score difference in treatment effect) between effects that are in the same direction for each gender, the analysis will be performed separately for men and for women. In the event of a treatment by gender interaction being observed, we will review study results by gender to determine the nature of the differences in treatment effects. If there is no interaction, the ANCOVA will be used to estimate the overall treatment effects across all clinical sites and both strata (genders). The primary analysis will be performed on the normal scores corresponding to percentile rank of each patient at baseline and follow-up.

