8.4 Changes from Protocol-Specified Efficacy Analyses

The primary efficacy analysis population has been renamed the “full analysis population” rather than the “intention-to-treat population” to avoid dispute over whether exclusion of patients for whom there are no follow-up visits or follow-up CT scans represents an imperfection in an “intention-to-treat” analysis plan or a different study population.

9 Interpretation of the Primary Outcome

Interpretation of the primary outcome analysis must be cognizant of N-TA³CT as a Phase IIb clinical trial. The primary outcome is based primarily on anatomical measurements instead of clinical events. Benefit in the primary outcome could influence physician behavior for off label use, but is not going to result in a labeled indication. In particular it cannot be expected that we will know whether or not doxycycline effects on abdominal aortic aneurysm diameter are associated with the occurrence of rupture or the diameter at which risk of rupture outweighs the risk associated with repair. Effects on rupture or mortality could be observed fortuitously, and would have to be interpreted as secondary outcomes. If the investigators reject the null hypothesis, they have a considerable responsibility to assure that they have not introduced bias and explain to the medical community their basis for believing that bias is not the reason for rejecting the null hypothesis. If the investigators fail to reject the null hypothesis, they have a considerable responsibility to assure that they have performed a sensitive test, i.e., not introduced bias through defects in study design (especially power calculation assumptions) and performance (especially adherence or missing data), and explain to the medical community their basis for believing that bias is not the reason for failing to reject the null hypothesis.

Interactions:

With gender: If there is a statistically significant interaction ($p \leq 0.05$) between the effect of doxycycline in men and the effect in women, there will be a search for explanations for the interaction. For example, adherence will be examined. The gender strata will be analyzed separately in the event of an important interaction. If there are important, non-significant differences between the gender strata, e.g., no effect in one stratum and a 40% effect size in the

Non-Invasive Treatment of Abdominal Aortic Aneurysm Clinical Trial

N-TA³CT

STATISTICAL ANALYSIS PLAN

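### The half-normal-score exemption in the gender-interaction rule is almost always inoperative, so it does not protect the pooled primary test, and SAP sections 8.1, 8.1.1 and 9 do not state one rule

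*SAP*

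**What the plan says.** Three places in the SAP govern what happens after the treatment-by-gender interaction is tested.

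- **Section 8.1** tests the interaction at two-sided 0.05 before the primary analysis. A significant result leads to separate analyses for men and women, "other than a small quantitative difference (less than half a normal score difference in treatment effect) between effects that are in the same direction". Otherwise the pooled ANCOVA gives the overall effect.
- **Section 8.1.1** (last paragraph, on degrees of freedom) uses the p-value alone. Above 0.05, only the treatment effect is tested. Below it, treatment and interaction are tested together in one model. There is no exemption for size or direction, and no separate analysis by sex.
- **Section 9** (Interactions, with gender) calls for a search for explanations after a significant interaction, and for separate analysis of the strata when the interaction is important. It does not define important. It then treats non-significant differences apart: "If there are important, non-significant differences between the gender strata, e.g., no effect in one stratum and a 40% effect size in the" other. These are analysed to the standard of secondary analyses, which section 4.2.2 sets at p < 0.01.

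Section 3.3.5 gives the effect against which a difference can be judged: "an assumed reduction of 40% in the mean increase in aneurysm diameter from 2.5 mm/year to 1.5 mm/year".

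**The concern.** The exemption in section 8.1 has a sensible purpose: to keep the powered pooled test when men and women differ in degree but not in direction. It can do so only if an interaction can be both significant and smaller than half a normal score. If the smallest significant interaction is already above that bar, the exemption never applies, and a chance same-direction interaction removes the pooled primary test.

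The bar is also called small, although on the plan's own design figures it is about as large as the whole effect the trial is powered to detect. With three differing rules, the choice between pooled and separate analysis could be argued after the data are seen.

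**Working it through.** **Inputs from the SAP.** Section 3.3.5: "greater than 90% power with a total sample size of 248 patients", a one-sided 0.025 test, and allowance for a "10% non-adherence rate in the doxycycline treatment group and for 15% of participants to have a missing two-year CT scans". Section 3.3.4: equal allocation. Section 4.2.2: final one-sided level 0.0247, which leaves the results below unchanged to three decimals. Section 8.1: interaction level two-sided 0.05, bar 0.5 normal score.

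**Inputs not in the SAP, assumed.** The SD of two-year growth (the SAP says "Additional details regarding the sample size and power calculations are contained in the protocol"), the share of women *p*, and the residual SD σ of the normal scores. Because no SD is given, the stated power cannot be reproduced independently; it can only be solved backwards.

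**Step 1. The planned effect in SD units.** Evaluable per arm: 124 × 0.85 = 105.4. For exactly 90% power:

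- d = (1.960 + 1.282) × √(2/105.4) = 0.447 after dilution by non-adherence, and 0.447/0.9 = 0.496 before it.
- At 95% power: 0.497 and 0.552. At 90% power with no loss to missing scans (124 per arm): 0.412 and 0.457.
- Consistency check (circular, since the SD is back-solved): SD 4.0 mm and a diluted effect of 2.0 × 0.9 = 1.8 mm need 104 per arm, and 208/0.85 = 245, close to 248.

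**Step 2. The scale of the bar.** The scores Φ⁻¹(k/249), k = 1 to 248, have SD 0.98, so half a normal score is about half an SD. The bar is thus about the whole planned effect. If 5-15% of patients hold worst ranks for events unrelated to treatment (assumed, SD 4.0 mm), the simulated planned effect falls to about 0.30-0.40 normal score, below the bar.

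**Step 3. The smallest interaction that can be significant.** With 1:1 allocation in each sex, SE = 2σ/√(N p(1−p)), and the smallest significant difference is 1.96 × SE. For N = 248:

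| Women | σ = 0.95 | σ = 0.98 | σ = 1.0 |
|---|---|---|---|
| 10% | 0.79 | 0.81 | 0.83 |
| 15% | 0.66 | 0.68 | 0.70 |
| 20% | 0.59 | 0.61 | 0.62 |
| 30% | 0.52 | 0.53 | 0.54 |
| 40% | 0.48 | 0.50 | 0.51 |
| 50% | 0.47 | 0.49 | 0.50 |

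Example: 1.96 × 2 × 0.98/√(248 × 0.15 × 0.85) = 3.842/5.623 = 0.68. Setting the result equal to 0.5 gives a crossing point near 39% women for σ = 0.98. Below it, every significant interaction exceeds the bar. Fewer analysed patients, or added variance from imputation, would raise the thresholds further.

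**Step 4. How often the pooled test is lost.** Sex-specific estimates were drawn as independent normals with a common true effect and SEs 2σ/√(N(1−p)) and 2σ/√(Np). With σ = 0.98, 15% women and a common effect of 0.3 to 0.5, about 2.3-2.8% of trials had a significant interaction with both estimates favouring doxycycline. The exemption rescued none of them. The rest of the 5% of significant results did not have both estimates favouring doxycycline.

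**Step 5. Dependence on σ.** Table 1 of section 8.1 ranks change in diameter, while the ANCOVA text subtracts a baseline score from a two-year score. If 24-month diameter were ranked, σ would be smaller: about 0.68 without events and 0.82 with 10% worst-ranked events (simulated, growth SD 4.0 mm assumed). At 15% women the threshold is then 3.92 × 0.68/5.623 = 0.47 or 3.92 × 0.82/5.623 = 0.57. So the exemption can operate on that reading, but only in a narrow band.

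**The case against.** Three objections carry weight.

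*Section 9 is not contradicted outright.* A reader might infer that the plan calls the same result small in one place and important in another. The documents do not support this. Section 9's example concerns non-significant differences, whereas the exemption acts only on significant ones; and no effect in one sex is not an effect in the same direction, although a near-zero favourable estimate would be. What remains is loose vocabulary and an undefined threshold for an important interaction.

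*The exemption does not commonly pool an effect present in one sex only.* A reader might infer this from the size of the bar. In simulation with a true effect in men only, it pooled 0% of trials when change is ranked (10-30% women). When 24-month diameter is ranked it pooled 0% at 10-15% women, at most 0.6% at 20% and at most 3.2% at 30%. Section 8.1 also has results reviewed by gender whenever an interaction is observed.

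*The loss is small and comes from the pretest.* Any interaction pretest at 0.05 is significant in 5% of trials with no true interaction, and deleting the exemption would not change the figure at 15% women. This stands as to size. It does not excuse the clause, whose purpose is to rescue the same-direction part of that 5%.

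**Conclusion.** The point holds in limited form. The bar of half a normal score is about the whole planned effect and, with a residual SD near 1 and up to about 30-40% women, lies below any interaction that could be significant. The exemption is therefore almost always inoperative. With 15% women and no true interaction, about 2-3% of trials would lose the pooled primary test although both sexes favour doxycycline. Separately, and without any assumption, sections 8.1, 8.1.1 and 9 give different triggers and, in section 8.1.1, a different analysis.

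The numerical part rests on a back-solved effect, an assumed share of women and an assumed residual SD; the protocol may narrow all three. The probability of harm is modest, but the change is worth making before unblinding because it settles which test is primary.

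**What to change.** In section 8.1, replace the half-normal-score exemption by direction:

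- If both sex-specific estimates (combined over imputations) favour the same arm, the pooled ANCOVA remains the primary test, whatever the interaction p-value.
- Only if the interaction is significant and the estimates point in opposite directions is the pooled test replaced by separate analyses.
- In every case, report the sex-specific estimates and the interaction beside the pooled result, to section 9's secondary standard.

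Reword the degrees-of-freedom paragraph of section 8.1.1 and the gender paragraph of section 9 to refer to this rule, and drop or define the important interaction.

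Lowering the size bar is not an alternative. Below about 0.45 it would lie under the smallest significant interaction even with 50% women (0.47-0.50 for σ of 0.95 to 1.0), so the clause would be just as inert.

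The cost is SAP wording only. The small downside is that a large same-direction difference is summarised by a pooled estimate, with the sex-specific estimates shown next to it.
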